### **17.3 Informed Consent Form**

Informed consent will be obtained in accordance with the Declaration of Helsinki, ICH GCP, US Code of Federal Regulations for Protection of Human Subjects (21 CFR 50.25[a,b], CFR 50.27, and CFR Part 56, Subpart A), the Health Insurance Portability and Accountability Act (HIPAA, if applicable), and local regulations.

The Investigator will prepare the informed consent form, assent and HIPAA authorization and provide the documents to the Sponsor or designee for approval prior to submission to the IRB/IEC. The consent form generated by the Investigator must be acceptable to the Sponsor and be approved by the IRB/IEC. The written consent document will embody the elements of informed consent as described in the International Conference on Harmonisation and will also comply with local regulations. The Investigator will send an IRB/IEC-approved copy of the Informed Consent Form to the Sponsor (or designee) for the study file.

A properly executed, written, informed consent will be obtained from each subject prior to entering the subject into the trial. Information should be given in both oral and written form and subjects must be given ample opportunity to inquire about details of the study. If appropriate and required by the local IRB/IEC, assent from the subject will also be obtained. If a subject is unable to sign the informed consent form (ICF) and the HIPAA authorization, a legal representative may sign for the subject. A copy of the signed consent form (and assent) will be given to the subject and the original will be maintained with the subject's records.

### **17.4 Publications**

The preparation and submittal for publication of manuscripts containing the study results shall be in accordance with a process determined by mutual written agreement among the study Sponsor and participating institutions. The publication or presentation of any study results shall comply with all applicable privacy laws, including, but not limited to, the Health Insurance Portability and Accountability Act of 1996.

### **17.5 Investigator Responsibilities**

By signing the Agreement of Investigator form, the Investigator agrees to:

1. Conduct the study in accordance with the protocol and only make changes after notifying the Sponsor (or designee), except when to protect the safety, rights or welfare of subjects.

2. Personally conduct or supervise the study (or investigation).
3. Ensure that the requirements relating to obtaining informed consent and IRB review and approval meet federal guidelines, as stated in § 21 CFR, parts 50 and 56.
4. Report to the Sponsor or designee any AEs that occur in the course of the study, in accordance with §21 CFR 312.64.
5. Ensure that all associates, colleagues and employees assisting in the conduct of the study are informed about their obligations in meeting the above commitments.
6. Maintain adequate and accurate records in accordance with §21 CFR 312.62 and to make those records available for inspection with the Sponsor (or designee).
7. Ensure that an IRB that complies with the requirements of §21 CFR part 56 will be responsible for initial and continuing review and approval of the clinical study.
8. Promptly report to the IRB and FDA CDER all changes in the research activity and all unanticipated problems involving risks to subjects or others (to include amendments and IND safety reports).
9. Seek IRB approval before any changes are made in the research study, except when necessary to eliminate hazards to the patients/subjects.
10. Comply with all other requirements regarding the obligations of clinical investigators and all other pertinent requirements listed in § 21 CFR part 312.

#### APPENDIX 1. SCHEDULE OF STUDY VISITS

	SCREENING VISIT 1 (Screen) a	STUDY1 VISIT 2 (Baseline) a	STUDY2 VISIT 3 (Month 3) a	STUDY3 VISIT 4 (MONTH 6)
Informed Consent	X			
Medical History	X			
Complete Physical Exam	X			
Abbreviated Physical Exam		X	X	X
Height	X			
Weight	X			
Vital Signs	X	X	X	X
Pregnancy Test (Serum)	X			
Hematology	X		X	X
Chemistry	X			X
Research blood stored	X	X	X	X
Neurological + ophthalmological exam with neurologist		X	X	X

MRI		X	X	X
Randomization	X			
Dispensing of Study Drug		X	X	
Counting of Returned Study Drug				X
Initiate Subject Diary	X			
Subject Diary Review		X	X	X
Concomitant Medication Review	X	X	X	X
Additional cognitive assessments		X	X	X
OCT	X	X		X
VEP	X	X	X	X
Vision testing (high, low contrast)		X	X	X
Cone contrast		X	X	X
VFQ		X	X	X
Questionnaires (MFIS, MSWS12, SF-36)		X	X	X
Assess likely side effects		X	X	X
EDSS		X	X	X
SDMT		X	X	X
Timed walking tests		X	X	X
ERG** (optional)	X			

Safety phone call at Week 6.

\*\* \*\*In rare cases during the initial visit, the patient may be asked to undergo an electroretinogram. This test measures the electrical response of the eye's light-sensitive cells, called rods and cones. These cells are part of the retina (the back part of the eye). This test is used to detect disorders of the retina. For this study, this option exists only to be used in cases where more information is needed to confirm a diagnosis of optic neuritis. The test is performed by placing numbing drops in the patient's eyes, so that there is no discomfort. Then, the patient's eyes are held open with a small device called a retractor. An electrical sensor (electrode) is placed on each eye and the electrical activity of the retina is recorded in response to light. The primary risk associated with the study is a temporary scratch of the surface of the cornea due to the electrode. Otherwise, there are no risks associated with this procedure.

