SAFETY EVALUATIONS	
Phone call at week 6 to see if patient is experiencing any unacceptable side effects.
 
When approximately 50% of patients have completed the study through Study Visit 2 (total visit 3), an interim analysis for safety will be conducted by the PI. Serious adverse events will be monitored by the committee on an ongoing basis throughout the study.
 
Incidence of adverse events.

PLANNED INTERIM ANALYSES	When approximately 50% of patients have completed the study through Study Visit 2 (total visit 3), an interim analysis for safety will be conducted by the PI. Serious adverse events will be monitored by the committee on an ongoing basis throughout the study.
STATISTICS Primary Analysis Plan	Data will be analyzed per protocol utilizing an intention to treat approach including all patients randomized to the study for the principal analysis. Loss to follow up will be accounted for using standard statistical methods. The principal analysis will be performed using mixed effects linear regression model controlling for clustering by eye.
Rationale for Number of Subjects	
With 25 patients per group the study has 90% power to detect a 50% relative reduction in latency with BZA compared to placebo at the 3-month outcome for group 1 assuming a two-sided test with alpha = 0.05.
 
Study size may be expanded to compensate for dropouts over the short study period. To maximize study efficiency and resource utilization these subjects will not be enrolled unless necessary.

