### 4 STUDY DESIGN

#### 4.1 Study Overview

This is a 6-month randomized, single center, double blinded, delayed start study in 50 patients with relapsing remitting multiple sclerosis and identified injury to the anterior visual pathway.

Patients will be randomized 1:1 into two groups: Group A and Group B. Group A will receive 180 days of Bazedoxifene while Group B will receive 90 days of placebo followed by 90 days of Bazedoxifene. Patients will receive two fixed oral tablets of 20mg Bazedoxifene (Conbriza) daily (to be taken at the same time). Patients will be permitted to remain on their standard disease modifying treatment during the course of the study.

Screening data will be reviewed to determine subject eligibility. Subjects who meet all inclusion criteria and none of the exclusion criteria will be entered into the study

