#### **5.3.7 Adverse Event Reporting Plan**

This study is investigator-sponsored and does not involve any outside sponsoring institution to which adverse events should be reported. Serious Adverse Events (SAEs) or unanticipated adverse events, therefore, will be reported internally to the UC San Francisco Committee on Human Research within 10 working days of the event's occurrence according to requirements outlined in the CHR's reporting guidelines.

All adverse events during this study will be recorded in real time in UCSF's HIPAA approved clinical database, REDCap. Recording such events in the same database each patient's trial-based visit records will allow for more efficient tracking and monitoring of all adverse events within the study.

In addition, an inventory of adverse events will be obtained at each visit.

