### **8.7 Measures of Treatment Compliance**

Subjects will be asked to keep a patient diary noting the day and date they take their study drug and any adverse events. They will be asked to bring their patient diary to each study visit along with all used and unused study drug containers.

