### **11 ADVERSE EXPERIENCE REPORTING AND DOCUMENTATION**

#### **11.1 Adverse Events**

An adverse event (AE) is any untoward medical occurrence in a clinical investigation of a patient administered a pharmaceutical product and that does not necessarily have a causal relationship with the treatment. An AE is therefore any unfavorable and unintended sign (including an abnormal laboratory finding), symptom or disease temporally associated with the administration of an investigational product, whether or not related to that investigational product. An unexpected AE is one of a type not identified in nature,

severity, or frequency in the current Brochure or of greater severity or frequency than expected based on the information in the Investigator's Brochure.

The Investigator will probe, via discussion with the subject, for the occurrence of AEs during each subject visit and record the information in the site's source documents. Adverse events will be recorded in the patient CRF. Adverse events will be described by duration (start and stop dates and times), severity, outcome, treatment and relation to study drug, or if unrelated, the cause.

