## 14 DATA SAFETY MONITORING

Safety Data Monitoring throughout the trial: Since this trial is a single-site trial and the overseeing Principle Investigator will be present throughout the trial, a Data and Safety Monitoring Board is not deemed necessary. The study investigator will be responsible for monitoring safety data and adverse events recorded in the patient file and will be responsible for reporting such events to the FDA and IRB.

Safety assessments will be throughout patient visits to ensure patient welfare and safety in daily activities.

Such assessments will include:

- Physical Examination
- Vital Signs
- Height and Weight measurements
- Pregnancy and Assessments of Fertility
- Ophthalmologic Examination

- Fatigue Assessment - Health Status Questionnaire & MFIS
- Pharmacokinetics/Blood tests to assess potential abnormal increase of liver enzymes and serum triglycerides
- Lab tests to assess level of BZA in patient plasma to ensure that they are not abnormal

The Investigator will meet with the study staff biweekly to review safety as well as efficacy data collected from patient visits and assess the safety of the visits and study outcomes.

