### 15.5 Interim Analysis

After each patient completes the Week 6 phone call, the side effects reported will be analyzed.

When 50% of patients have completed the study through Study Visit 2 (total visit 3), an interim analysis for safety will be conducted by the PI.

Serious adverse events will be monitored by the committee on an ongoing basis throughout the study.

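### The only scheduled safety call falls in Stage 1, so delayed-start patients have no scheduled safety enquiry for about 90 days after their first bazedoxifene dose

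*Combined protocol and SAP*

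**What the plan says.** The between-visit safety call appears in three places, each time as one call. Appendix 1 has "Safety phone call at Week 6". The synopsis gives its purpose: "Phone call at week 6 to see if patient is experiencing any unacceptable side effects". Section 15.5 says what is done with the answers: "After each patient completes the Week 6 phone call, the side effects reported will be analyzed". The visit lists in Section 10 do not mention it.

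Section 4.1 sets the exposure sequence for the delayed-start arm: "Group B will receive 90 days of placebo followed by 90 days of Bazedoxifene". Appendix 1 has study drug dispensed at Baseline and Month 3, so Group B receives its first BZA at Month 3.

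The other planned enquiries are tied to visits. Section 5.3.7 says "In addition, an inventory of adverse events will be obtained at each visit", and Section 11.1 says "The Investigator will probe, via discussion with the subject, for the occurrence of AEs during each subject visit". Patients keep a diary of doses and adverse events, which staff see at visits; Section 8.7 says "They will be asked to bring their patient diary to each study visit along with all used and unused study drug containers". The regular staff review in Section 14 works from data already in hand: "The Investigator will meet with the study staff biweekly to review safety as well as efficacy data collected from patient visits".

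**The concern.** The sponsor judged that a mid-stage call was worth making, to find side effects that patients cannot accept, and undertook to look at the answers. For Group A that call comes during first exposure to BZA. For Group B it comes during placebo, and nothing equivalent follows once BZA begins. The check therefore misses first exposure in half of the randomised patients.

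What is at stake is how soon staff learn of a problem. A side effect that begins in a Group B patient shortly after Month 3 may not be asked about for the rest of the stage. This matters because tolerability in this population, with special attention to fatigue, is a key secondary objective (Section 3.2). The exclusions for thromboembolism, thrombophilia and immobility also show that the protocol recognises risks for which early enquiry is sensible. Other layers are thin: Section 14 dispenses with a data and safety monitoring board, and Appendix 1 schedules chemistry only at Screening and Month 6.

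**Working it through.** The plan gives no figure of its own on this point, so the check is a day count on the schedule.

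**Inputs**
- Visits at nominal days 0 (Baseline), 90 (Month 3) and 180 (Month 6), from Section 4.1 and Appendix 1. No windows are given for Months 3 and 6.
- Baseline is 14 ± 2 days after Screening (Section 10.1, which labels Screening as Week 0).
- Week 6 = 42 days. What it is counted from is not stated, so both readings are tried.
- 25 patients per group (Section 15.6).
- Dropout before Month 3 is not given. It is assumed at 0%, 10% and 20%.

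**Step 1: when the call falls**
- Counted from Baseline: day 42.
- Counted from Screening: 42 − (14 ± 2) = day 26 to 30 after Baseline.

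Both come before day 90, so Group B is on placebo under either reading. The call precedes Group B's first BZA dose by 90 − 42 = 48 days, or by 60 to 64 days.

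**Step 2: longest interval without a scheduled enquiry in the first 90 days on BZA**

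| | Enquiries, in days from first BZA dispensing | Intervals (days) | Longest (days) |
|---|---|---|---|
| Group A, call counted from Baseline | 42, 90 | 42, then 90 − 42 = 48 | 48 |
| Group A, call counted from Screening | 26–30, 90 | 26–30, then 60–64 | 60–64 |
| Group B, as planned | 90 | 180 − 90 = 90 | 90 |
| Group B, with a call 42 days after Month 3 dispensing | 42, 90 | 42, then 48 | 48 |

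The added call would fall at about study day 90 + 42 = 132.

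**Step 3: other contacts between Month 3 and Month 6**
- *Diary:* kept by the patient and reviewed at visits.
- *Adverse event inventory and investigator questioning:* at visits only.
- *Biweekly staff meeting:* reviews data from visits and adds no patient contact.
- *Drug re-supply (Section 8.4.2):* happens only if stock is near expiry, may be by post, and is not described as a safety contact.
- *Continuous adverse event and SAE collection (Sections 5.3.7, 9.1.7 and 11.2.1):* runs throughout, but in this interval depends on what the patient volunteers.
- *Early discontinuation and safety follow-up visits (Sections 12.1 and 14):* arise only once a patient has stopped treatment.

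None of these is a scheduled enquiry by staff.

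**Step 4: size**
- Group B patients affected: 25 at no dropout, 25 × 0.9 = 22.5 at 10%, 25 × 0.8 = 20 at 20%.
- Planned BZA patient-days: Group A 25 × 180 = 4,500; Group B 25 × 90 = 2,250; Group B's share 2,250 / 6,750 = 33%. This measures exposure, not risk.

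**The case against.** The strongest reply is that little is lost. No text promises a mid-stage contact in Stage 2, so the plan breaks no rule of its own. The controlled tolerability comparison is Stage 1, where both groups get the same call. Adverse events are tabulated by treatment group (Section 15.4), a term Section 8.1 uses for the assigned groups, so those tables are not distorted. The background cites a two-year trial with 840 participants on 40 mg and a three-year trial with 1,872, both with good tolerability, and the exclusions remove patients at raised thromboembolic and hepatic risk. The diary is a prospective record, serious events are collected to the final visit, and a patient who cannot tolerate the drug may stop at any time and is then seen. All of this stands, and it limits the point to delay in learning of events. It does not remove the delay: these routes wait for the patient to act, and the cited trials were not in MS.

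The interim safety analysis does not fill the gap either. It is triggered when about half the patients have completed Month 3, so it is not timed to Group B's BZA exposure.

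The 33% share also does not isolate the gap, because Group A's Stage 2 is another 25 × 90 = 2,250 patient-days without a call. By then, however, Group A has been asked about side effects on BZA twice, by phone and at Month 3. No event rate is available from which to estimate how many events would be found late.

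Finally, Appendix 1 carries a superscript *a* on Visits 1 to 3 with no matching note. The unmarked line about the call could be that note, which would tie a call to both dispensing visits. This is speculative: the marker is also on Screening, where no drug is dispensed, and the synopsis and Section 15.5 both describe one call.

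**Conclusion.** The concern holds. As written, Group B has no scheduled safety enquiry by staff from first BZA dispensing at Month 3 until Month 6, nominally 90 days. The longest such interval in Group A's first 90 days on BZA is 48 days, or 60 to 64 if Week 6 is counted from Screening. Up to 25 patients are affected, or about 20 to 23 at an assumed 10 to 20% dropout before Month 3.

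The conclusion rests on visits at their nominal days and on the call being a single one, as all three places word it. It does not depend on what Week 6 is counted from. The consequence is later detection at first exposure, not bias and probably not lost events. Making the call to both groups in Stage 1 is right for the blind; what is missing is its counterpart in Stage 2. This is an inexpensive improvement that should be made, not the correction of an error.

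**What to change.** Make the same blinded safety call to all patients in both groups six weeks after Month 3 dispensing. Calling both groups preserves the blind. Count each call from its own dispensing visit (Baseline and Month 3), which also settles what Week 6 means. List both calls in Section 10 and Appendix 1, and extend the side-effect review in Section 15.5 to the second call. With both calls counted from dispensing, the longest interval in the first 90 days on BZA becomes 48 days in both groups.

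The cost is at most about 50 short calls by existing staff (50 × 0.9 = 45 or 50 × 0.8 = 40 at the assumed dropout) and a schedule amendment, with no new procedure. The downside is some staff time and somewhat more mild events recorded in Stage 2.
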